e Vital signs will include sitting and standing measurements of blood pressure and heart rate, respiratory rate, and oral body temperature. All clinic visits will have predose vitals. Visit 3 (Day 1) and Visit 7 (OL Day 1) and any clinic visit that a subject titrates up, vitals will also be collected 1 (± 15 min) hour and 2 hours (± 15 min) post dose, additional medical assessments can be performed as needed per investigators discretion.

f If female, blood samples for follicle stimulating hormone (FSH) will be collected.

 $^{^{\}rm g}$ If female, blood sample will be collected for β -hCG test.

h Blood samples for determination of plasma SEP-363856 and SEP-363854 concentrations will be collected predose (before study drug administration) and between 1-3 hours post dose on Day 1. One sample will be collected on Day 43 (12 ± 4 hours after the Day 42 dose), Day 71 (OL Day 29) (12 ± 4 hours after the Day 70 [OL Day 28] dose), and Day 127 (OL Day 85) (12 ± 4 hours after the Day 126 [OL Day 84] dose). The time and date of food intake will be recorded on Day 43 when blood samples are collected for determination of plasma SEP-363856 concentrations.

NOTE: Subjects will remain at the clinical site on Day 1 and Visit 7 (Day 43; OL Day 1) until the Investigator deems it appropriate to discharge the subject.

NOTE: Efforts will be made to ensure that the subject's caregiver remains the same for all study visits.

NOTE: All double-blind post-Baseline visits will have a window of \pm 2 days relative to the date of the Baseline visit (Visit 3). OL study day is based on days from the OL baseline Visit 7.

NOTE: For this study 1 week is defined as 7 days and 1 month is defined as 4 weeks (28 days).

NOTE: The SAPS-PD, CGI-S, MMSE, UPDRS II, UPDRS III, and neurological exam should be performed during the subject's on-periods (ie, at a time when the subject shows no clinical evidence of worsening in their Parkinson's symptoms, as determined by the site investigator). The NPI is administered to the caregiver only and should be completed referencing the subject's on-period.

¹ Urine drug screen may be ordered at other visits as deemed clinically appropriate. These results should be discussed with the Medical Monitor.

C-SSRS Baseline/Screening version will be administered for Visit 1; all other visits will administer the C-SSRS Since Last Visit version.

^k Post Screening Serum prolactin results will remain blinded.

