6.3. Safety Endpoints

Double Blind Period:

- The incidence of AEs, SAEs, and AEs (or SAEs) leading to discontinuation during the double-blind period.
- Absolute values and changes from DB Baseline in clinical laboratory tests (hematology, serum chemistry, urinalysis), and clinical evaluations (vital signs, body weight, BMI, blood pressure [supine and standing], heart rate [supine and standing], and 12-lead ECGs).
- Frequency of subjects with suicidal ideation or suicidal behavior using the C-SSRS during the double-blind period.

Open-label period:

- The incidence of AEs, serious adverse events (SAEs), and AEs (or SAEs) leading to discontinuation during the open-label (OL) extension and overall.
- Absolute values and changes from DB and OL Baseline in clinical laboratory tests (hematology, serum chemistry, urinalysis), and clinical evaluations (vital signs, body weight, BMI, blood pressure [supine and standing], heart rate [supine and standing], and 12-lead ECGs).
- Frequency of subjects with suicidal ideation or suicidal behavior using the C-SSRS during the open-label extension and overall.

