11.4.3. Vital Signs

Blood pressure, respiratory rate, oral temperature, and pulse rate should first be taken with the subject in the supine position after resting for ≥ 5 minutes. Blood pressure and pulse rate will be taken again after standing for 2 to 4 minutes. The same arm should be used during each assessment of blood pressure and pulse rate throughout the study. If a subject develops symptoms consistent with orthostatic hypotension (light-headedness, dizziness, or changes in sensorium upon standing) at any point, his or her supine and standing blood pressure and pulse

rate should be collected at that time in the manner described above. Vital signs will be obtained prior to clinical laboratory collection and performance of an ECG.

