16.4.1. ORTHOSTATIC EFFECTS

Orthostatic hypotension is defined as a decrease of \geq 20 mmHg in systolic blood pressure or \geq 10 mmHg in diastolic blood pressure after the subject had been standing for at least 2 to 4 minutes, compared to the systolic blood pressure and diastolic pressure measured in the supine position, respectively.

Orthostatic tachycardia is defined as a heart rate increase of \geq 20 beats per minute (bpm) and a heart rate of >100 bpm after the subject was standing for at least 2 to 4 minutes, compared to the heart rate measured in the supine position.

The number and percentage of subjects with orthostatic hypotension and orthostatic tachycardia will be summarized for baseline and the overall post-baseline period including follow-up visit, as well as by visit for DB period and OL period. This will be presented for systolic hypotension, for diastolic hypotension, and for both, including mean change from baseline, any orthostatic hypotension or tachycardia events that occurred at the early termination visit will be assigned to the next planned visit (as specified in Section 6.4).

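### Footnote e to the visit schedules calls for sitting and standing vital signs, while the procedure, safety endpoints and SAP orthostatic definitions need supine and standing readings

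*Protocol*

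**What the plan says.** Protocol Tables 2 and 3 share footnote e, which gives the posture for the scheduled readings: "Vital signs will include sitting and standing measurements of blood pressure and heart rate". The same footnote covers Day 1, open-label Day 1 and every up-titration visit, where "vitals will also be collected 1 (± 15 min) hour and 2 hours (± 15 min) post dose".

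Protocol Section 11.4.3 sets a different pair. The readings "should first be taken with the subject in the supine position after resting for ≥ 5 minutes", and then "Blood pressure and pulse rate will be taken again after standing for 2 to 4 minutes".

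The safety endpoints in protocol Section 6.3, and the matching list in the synopsis, are absolute values and changes from baseline for "blood pressure [supine and standing], heart rate [supine and standing".

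SAP 16.4 lists supine and standing systolic pressure, diastolic pressure and pulse rate, with no sitting variable. SAP 16.4.1 defines orthostatic hypotension as a fall of at least 20 mmHg systolic or 10 mmHg diastolic on standing, "compared to the systolic blood pressure and diastolic pressure measured in the supine position". Orthostatic tachycardia likewise takes the supine heart rate as its reference.

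**The concern.** One posture instruction contradicts all the others, and it sits where a site coordinator is likely to look first. The synopsis and Section 7.1 send sites to Table 2 for visit procedures. Section 11.9 sends them to the tables for a summary and to 11.9.1 to 11.9.12 for detail. Those visit sections ask for vital signs or orthostatic vital signs and name no posture. On that route footnote e is the only posture instruction a site meets, and it does not refer to Section 11.4.3.

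What is at stake is the haemodynamic safety data. Protocol Section 4.3 reports hypotension and orthostatic hypotension in earlier studies, including one hypotension event assessed as serious. Section 7.3.1 says there are no data in patients aged 65 or over, and Section 7.3.2 that the drug had not been given in Parkinson's disease before this study. Orthostatic readings are also part of the two-hour clinic observation after the first dose and after each up-titration. In such a study the posture in which readings are taken should not depend on which page a site consults.

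**Working it through.** The plan states no figure for this point, so the check compares the texts.

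**Step 1: where a posture is stated.**

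| Place | Posture |
|---|---|
| Protocol Tables 2 and 3, footnote e | sitting and standing |
| Protocol synopsis, safety endpoints | supine and standing |
| Protocol 6.3 | supine and standing |
| Protocol 11.4.3 | supine, then standing |
| SAP 16.4, variables and flag criteria | supine and standing |
| SAP 16.4.1 | standing, with supine as reference |

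One place says sitting and five use supine. The study design and visit text (protocol 7.1 and 11.9) gives no posture for its vital-sign or orthostatic checks. No rule sets precedence.

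**Step 2: how many visits are covered.** Vital signs are scheduled at Visits 1 and 3 to 7 in Table 2 (6 visits) and at Visits 8 to 14 in Table 3 (7 visits), so 6 + 7 = 13. The post-dose checks come on top of these.

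**Step 3: what can be derived if a site takes only the readings in footnote e.**

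| Planned output | Derivable? |
|---|---|
| Standing pressure and pulse: values and changes from baseline | yes |
| Standing flags for potentially clinically significant values | yes |
| Supine pressure and pulse: values and changes from baseline | no |
| Supine flags (value limit plus change from baseline) | no |
| Orthostatic hypotension (fall from supine) | no |
| Orthostatic tachycardia (rise of at least 20 bpm from supine, with rate above 100 bpm) | no; the standing rate is known but the rise from supine is not |
| Respiratory rate, temperature, weight, BMI | yes; the SAP gives them no posture |

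**Step 4: what the SAP would do with sitting readings.** It has no variable and no rule for them. They would either drop out of the supine-based outputs, or be used in place of supine values, which changes the reference for the orthostatic fall.

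**Step 5: how a difference between sites would spread.** About 36 subjects at about 24 sites is 36/24 = 1.5 subjects per site. A difference in site practice would therefore act almost at the level of the single subject.

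**Step 6: size.** The documents give neither the share of sites that would follow footnote e nor any difference between sitting-to-standing and supine-to-standing changes. The number of missing or misclassified subjects cannot be computed.

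**The case against.** The best reply is that a careful site would still do the right thing. Sections 11 and 11.9 call Tables 2 and 3 a summary, and Section 7.1 cites Section 11 alongside them. Footnote e gives no rest time and no standing time. Section 11.4.3 alone gives a method that can be carried out: at least 5 minutes of rest, then 2 to 4 minutes standing, using the same arm. It repeats supine and standing for subjects with symptoms. The visit text speaks of orthostatic vital signs. The case report form is not in the documents and may well offer only supine and standing fields. The orthostatic results are counts and percentages, and SAP 16 plans no between-group safety tests unless specified. All of this stands, and it makes the problem a risk and not a demonstrated error. It does not remove the contradiction, because no passage tells a site to prefer 11.4.3.

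Three stronger readings are tempting, and the documents do not support them.

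- A reader might infer that the safety endpoints, Section 11.4.3 and the SAP all rest on a supine-to-standing change, so that nothing can be derived from footnote e readings. Only SAP 16.4.1 defines such a change. Section 6.3 lists values and changes from baseline, and Section 11.4.3 prescribes two readings. The standing outputs survive.
- A reader might take 1/24 = 4.2 or 1/12 = 8.3 percentage points as the size of the error. That is what any one subject contributes to a rate in an arm of 24 or 12. It is not an estimate of misclassification.
- A reader might assume that sitting values will be recorded as supine. Without the case report form this can be neither shown nor excluded.

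**Conclusion.** The point holds as an internal inconsistency: footnote e is wrong as written against the procedure, the endpoints and the SAP. If a site follows it literally, that site supplies no supine values, and its subjects' supine summaries, supine flags and orthostatic outcomes cannot be derived as defined. How many subjects this touches is unknown and could be none. That depends on site practice and on the case report form, neither of which the documents show. Standing values and the primary SAPS-PD analysis are not affected. The matter is more than clerical because planned safety outcomes, on a risk that the protocol itself names, depend on the posture.

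**What to change.** - Reconcile footnote e with protocol Sections 11.4.3 and 6.3 and SAP 16.4/16.4.1, either by changing sitting to supine in the footnote or by replacing its posture wording with a cross-reference to Section 11.4.3. This aligns the measurement with the planned variables and proposes no rule for managing subjects after dosing.
- Send sites a clarification so that one posture pair applies at the scheduled and post-dose readings.
- Add a sentence to SAP 16.4.1, before unblinding: where source records show that a reading was taken sitting, it is not treated as supine in the orthostatic derivation. Nothing in the documents shows that actual posture is recorded, so this rule can act only where source records exist.

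The text change is one word or one cross-reference. It is still a protocol revision, which under protocol Section 17.5 needs written approval from the sponsor and the IRB/IEC. Leaving sitting readings out will also create some missing orthostatic data. SAP 7.3 does not impute missing safety data, so the report should give the number of subjects with a valid supine and standing pair as the denominator.

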3. LIST OF ABBREVIATIONS AND DEFINITIONS OF TERMS

The abbreviations and the definition of key study terms used in the clinical study protocol are provided in Table 4 and Table 5.

Table 4: List of Abbreviations

Abbreviation	Full Form
AE	Adverse event
ALT	Alanine aminotransferase
aPTT	Activated partial thromboplastin time
ANCOVA	Analysis of covariance
AST	Aspartate aminotransferase
ATC	Anatomical Therapeutic Chemical
β-hCG	Serum human chorionic gonadotropin
BMI	Body mass index
BOLD	Blood oxygen level dependent
BUN	Blood urea nitrogen
CAP	College of American Pathologists
CDR	Clinical data repository
CFR	Code of Federal Regulations
CGI-I	Clinical Global Impression – Improvement
CGI-S	Clinical Global Impression – Severity
CLIA	Clinical Laboratory Improvement Amendments
CNS	Central nervous system
CRF	Case report form
CRO	Contract research organization
CS	Clinically significant
C-SSRS	Columbia-Suicide Severity Rating Scale
CYP	Cytochrome
DA	Dopamine
ECG	Electrocardiogram
EDC	Electronic data capture
EEG	Electroencephalogram

Table 4: List of Abbreviations (Continued)

Abbreviation	Full Form
ET	Early termination
FDA	US Food and Drug Administration
fMRI	functional magnetic resonance imaging
FSH	Serum follicle stimulating hormone
GCP	Good Clinical Practice
5-HT	5-hydroxytryptamine (serotonin)
HbA _{1c}	Serum or plasma glycosylated hemoglobin
HIV	Human immunodeficiency virus
ICH	International Conference on Harmonization
IEC	Independent Ethics Committee
IND	Investigational New Drug
IPD	Important protocol deviation
IRB	Institutional Review Board
IXRS	Interactive voice/web response system
LOCF	Last observation carried forward
LIMS	Laboratory information management system
MAR	Missing at random
MedDRA	Medical Dictionary for Regulatory Activities
MID	Monetary incentive delay
mITT	Modified Intention-to-Treat
MMRM	Mixed Model for Repeated Measures
MMSE	Mini Mental State Examination
MTD	Maximum tolerated dose
N2	NREM sleep stage 2
N3	NREM sleep stage 3
NCS	Not clinically significant
NE	Neurological examination
NPI	Neuropsychiatric Inventory
NREM	Non-rapid eye movement sleep
OL	Open-label
PD	Parkinson's disease

Table 4: List of Abbreviations (Continued)

Full Form
Parkinson's disease psychosis
Physical examination
Pharmacogenomic(s)
Pharmacokinetic(s)
Population pharmacokinetics
Time between P wave and QRS in electrocardiography
Polysomnography
Preferred term
Partial thromboplastin time
Pharmacovigilance
Once daily
Electrocardiographic wave (complex or interval)
Electrocardiographic interval from the beginning of the QRS complex to the end of the T wave
QT interval corrected for heart rate
Rapid Eye Movement (REM) Sleep Behavioral Disorder
Rapid Eye Movement Sleep Behavior Disorder Questionnaire
Rapid eye movement
Respiration rate
Serious adverse event
Statistical analysis plan
Scale for Assessment of Positive Symptoms
Scale for Assessment of Positive Symptoms – Parkinson's Disease
Scales for Outcomes in Parkinson's Disease Sleep Scale – Daytime Sleepiness
Scales for Outcomes in Parkinson's Disease Sleep Scale – Nighttime Sleep Quality
System organ class
trace amine associated 1 receptors
United States, United States of America

Table 4: List of Abbreviations (Continued)

UPDRS	Unified Parkinson's Disease Rating scale
USP	United States Pharmacopeia
WBC	White blood cell
WHO-DD	World Health Organization Drug Dictionary
YOPD	Young onset Parkinson's disease

Table 5: Definition of Key Study Terms

Terms	Definition of terms
CRF	A printed, optical, or electronic document designed to record all of the protocol required information to report to the Sponsor for each study subject.
Screened Subject	Any subject who signed the study specific informed consent.
Screen Failures	Any subject who signed the study specific informed consent but either failed to meet study requirements during screening or met study requirements at screening but was not enrolled/randomized.
Study Drug (or Study medication) or Investigational Product	Term to cover investigational drug and placebo.
Treatment Period	The period of the study in which the double-blind study drug is administered.
Randomized Subject	Any subject who was randomized into the treatment period of the study and was assigned a randomization number.
Enrolled Subject	Any subject who was successfully screened and enrolled into the pre-randomization period of the study.
Randomization Failures	Any subject who was enrolled but not randomized.
Completed Subject	Any subject who completed the study by participating throughout the duration of the study, up to and including the last in-clinic visit.
Early Termination Subject	Any subject who was successfully screened and randomized into the treatment period of the study, but did not complete the study.
End of Treatment	The day that the subject receives protocol-defined last dose of the study drug. This may or may not include a taper period.
End of Study	The day that the subject completes the study per the study design.
1 Week	Defined as 7 days.
1 Month	Defined as 28 days.
On-Period	Defined as a time when the subject shows no clinical evidence of worsening in their Parkinson's symptoms, as determined by the site investigator.

4. INTRODUCTION

4.1. Background

Parkinson's disease (PD) is a chronic neurodegenerative disorder that affects motor control. It is the second most common neurodegenerative disease after Alzheimer's disease and affects approximately 1 million people in the United States (US) and 7 million people globally. The mean age of onset is around 60 years, although 5 to 10% of cases, classified as young onset PD (YOPD), begin between the ages of 20 and 50. The main pathological characteristic of PD is neuronal cell death in the substantia nigra, which leads to loss of dopamine, a critical neurotransmitter involved in movement control. PD has been increasingly recognized as having a multitude of non-motor symptoms including psychosis, cognitive impairment, and dementia mood disturbances, fatigue, apathy, and sleep disorders.

Parkinson's disease psychosis (PDP) is a common and debilitating condition. Symptoms commonly include visual hallucinations, delusions (paranoia) and illusions (misperception of objects). Estimates on the incidence of PDP vary widely depending on the study from 40% (Fénelon-2000, Chou-2005) to as high as 60% (Fénelon-2010 and Riedel-2010). The risk for PDP increases with disease duration and severity, as well as with declines in cognitive function, increased age, depression, and sleep disorders (Papapetropoulous-2005). PDP has also been associated with poorer quality of life, increased morbidity and mortality in addition to increased caregiver burden and nursing home placement (Aarsland-2000). Underlying pathogenesis remains uncertain although psychotic symptoms are likely attributable in part to the effects of dopamine agonists used in the treatment of PD. Dopaminergic agonists can stimulate limbic dopamine D2 receptors to produce psychotic symptoms, in much the same way as in schizophrenia. Although lowering the dose of dopamine agonists can alleviate the symptoms of PDP, they can also worsen the motor symptoms associated with PD. Disturbances in 5-HT (5-hydroxytryptamine [serotonin]), including 5-HT_{2A}, 5-HT_{1A}, 5-HT_{2C} receptors, may also contribute to PDP as well other behavioral disorders associated with PD such as depression and anxiety (Ballanger-2010).

Treatment of psychosis involves the use of typical or atypical antipsychotic medications, which act predominantly as dopamine D_2 receptor antagonists. For PDP, such pharmacological treatment is fraught with risk as D_2 antagonism may also target the symptomatic dopamine (DA) replacement therapy used in PD and potentially worsen motor symptoms. In addition antipsychotics carry a boxed warning against their use in elderly patients with psychosis due to increased mortality and morbidity (Friedman-2010). Two agents commonly used to treat PDP are clozapine and quetiapine as off-label use.

Clozapine has higher affinity for serotonin 5-HT_{2A} receptors than for D₂ receptors. Low-dose clozapine (≤ 50 mg) has been demonstrated as an effective treatment (The Parkinson Study Group-1999); the dose levels used in PDP are significantly lower than the therapeutic dose used for the treatment of schizophrenia (300 - 900 mg). The use of low-dose clozapine in PDP, however, is limited by its adverse effects, in particular, agranulocytosis, which is not dose related (Thomas-2010).

Quetiapine is an atypical antipsychotic, similar in structure to clozapine. It exhibits strong antagonism of $5HT_2$ receptors and weak antagonism of D_2 receptors. The American Academy of

Neurology's task force on PD treatment recommends quetiapine as a treatment option after clozapine has been considered. The use of low-dose quetiapine in PDP is also limited by its adverse effects, in particular, sedation and metabolic changes including hyperglycemia, dyslipidemia and weight gain.

NuplazidTM (pimavanserin), a selective 5-HT_{2A} inverse agonist, is the first treatment approved for PDP indication by the US Food and Drug Administration (FDA) in April 2016. A recently completed clinical study investigating the use of pimavanserin in subjects with PDP demonstrated significant improvements in the primary endpoint as measured by the SAPS-PD (Scale for Assessment of Positive Symptoms – Parkinson's Disease) and in several secondary and exploratory outcomes, including the Clinical Global Impression – Improvement (CGI-I) and Clinical Global Impression – Severity (CGI-S), night-time sleep, daytime wakefulness and caregiver burden (Cummings-2014). Pimavanserin was well-tolerated; however, there was an imbalance of serious adverse events including death in the pimavanserin group compared to the placebo group although no particular (serious adverse event) SAE was more prominent than others. In addition, pharmacokinetic (PK) studies showed that pimavanserin did not reach steady-state plasma levels until after 10 to 14 days of repeated daily administration in PD patients (Hacksell-2014) while improvement in psychotic symptoms was not observed until 2 to 3 weeks after initiation of treatment (Cummings-2014).

Effective agents for PDP are scarce and serious adverse side effects associated with their use are limiting. Although pimavanserin appears to be a promising agent, concerns remain for its modest efficacy, safety and its delay in onset of action, which together may limit its use. The development of effective and well-tolerated treatments for patients with PDP is therefore warranted.

